3.1. Sample Size

Subjects will undergo an initial screen and device demonstration (screening arm) to determine their suitability for an extended trial of the device (extended arm). The target number of subjects for the extended arm is 60 subjects.

Power analysis indicates that in a single tailed test with an alpha level of .05 and a power of .95, the relationship between anticipated effect size and the required sample size is shown in the chart at left. As indicated if we assume an effect size in the range 0.40 – 0.45¹², an appropriate n=60 (ten Study subjects per site).

¹¹ The term “functional visual performance” describes the wearer’s ability to perform various Activities of Daily Living (ADL) with better efficacy and speed than using habitual assistive technology devices. In some cases, because of the hands-free, variable distance, and portable attributes of eSight Eyewear, it is hypothesized that certain ADLs may be possible which were previously impossible or very difficult for certain subjects.

¹² This higher than typical anticipated effect size is an appropriate assumption for this Study design, because of prescriptive inclusion criterion (i.e.: not random population).

About $\frac{1}{3}$ to $\frac{1}{2}$ of subjects who fall into the acuity and visual field inclusion criterion described in Section 3.2 below, demonstrate acute objective improvement and an immediate aptitude with the device. Therefore, we anticipate a total of 150-200 to be enrolled in screening arm of the study, from which 60 will be selected to participate in the extended arm, a three month take-home trial of the device. We expect attrition to be low due to the rigorous screening process for participation.¹³

In addition to a clinician's unit, which incorporates trial lens frames and other unique features for fitting and demonstration, each Site will receive devices for Subjects as they are required. The Site and eSight can, at any time, agree to deploy additional devices to accelerate the collection of data.

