Step 2.03 Baseline eSight-8 Questionnaire: Third Party Surveyor will work with the subject to complete seven QoL type questions which will provide predictive insights regarding their affinity with the eSight device.

Step 2.04 Advancement Decision: Based on the Subject's responses to 2.02 and 2.03 above the Eyecare Physician will determine whether or not the Subject ought to proceed through the Protocol.

Note: While not an explicit inclusion criterion, there are seven questions on the VA LV VFQ-48 items identified in red (2, 3, 5, 12, 14, 19, 45) for which the eSight Eyewear device has been shown to be particularly effective. If a subject scores four or more of these items as "moderately difficult" or "extremely difficult", they will be considered a strong candidate.

STEP 3: Clinic Visit – LV Assessment & eSight Demonstration

Subjects will also be asked to complete a series of supervised activities to establish a baseline of their visual function and functional visual performance *without* eSight Eyewear¹⁹.

Duration: 2-3 hours.

Steps 3.01 through 3.04 may be administered by a Research Assistant or a similarly suitable staff person at the clinic (e.g.: CLVT, OT, etc.).

Step 3.01 Low Vision Rehabilitation Goals: The CRF form identifies five ADLs, prioritized by the subject, which they wish do (or do better). It also asks how satisfied they are currently with their ability to perform this task, and how important this task is to their day-to-day quality of life. The purpose of this step is provide the subject with specific goals that they can work to achieve (or improve) using eSight Eyewear over the course of the study.

¹⁷ In the case of Johns Hopkins University Wilmer Eye Institute, research assistants from the institute will conduct Step 2. These research assistants will be dis-associated from the PI and other researchers who have face-to-face interaction with the subject.

¹⁸ Using the VA LV VFQ-48 and LV VFQ-20 in Low Vision Rehabilitation, Stelmack, Massof, Optom Vis Sci. 2007 Aug;84(8):705-9.

¹⁹ Because we intend to deploy standardized ADL measures, it may be possible to compare our findings directly to some other interventions (e.g.: Haymes, Johnston, & Heyes, 2001).

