- **Subject’s Unit:** If the subject is deemed a suitable candidate for an extended evaluation period, they will receive a unit with the user interface customized for them, along with their prescription lenses incorporated, if applicable.
- **Materials for In-Clinic ADL Testing:** Telephone book, kitchen ingredients, etc.

10. Analysis

Some of the data gathered through the course of this study is subjective, and will be used by eSight to prioritize ongoing improvements to the device.

The minimum objective data that will be reported is acuity, contrast, reading speed, without eSight Eyewear at the beginning of the trial, and with eSight Eyewear at its conclusion.

Further objective data is the comparison between the initial VFQ, and RAND SF-36 scores, and the change, if any, in score at the conclusion of the study.

Data analysis will be conducted using IBM SPSS Statistics version 22. The data will be pooled from all testing sites by the Study Manager. Before merging of the data, any systematic differences among testing sites will be assessed. Should such differences exist, they will be considered in subsequent analyses.

Repeated measures Analysis of Variance (ANOVA) and t-tests will be used to compare the effect of the eSight devices on all dependent variables that adhere to the assumptions of parametric data analysis (continuous variables, normal distribution etc.). Categorical variables or those who do not adhere to parametric assumptions will be compared using repeated-measures non-parametric techniques (e.g. Friedman Test). Qualitative data will be analyzed using qualitative description (Sandelowski, 2000).

³⁸ Requires 22” monitor with HDMI input. To be provided by eSight in the event that the study location does not have one available.

The eSight device contains an electronic logging capability, wherein daily on-time hours, and user commands (e.g.: zoom in/out, focus distance, increase/decrease contrast, etc.) are saved to an SD card. No images or video or other information that may personally identify the subject is recorded. These electronic logs may be used to validate user reported usage data³⁹.

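### The baseline VFQ-48 also helps decide who advances, so part of its before/after change may be regression to the mean

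*Combined protocol and SAP*

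**What the plan says.** - **Section 4.1, Step 2.02** labels the telephone VFQ-48 as the baseline. No other VFQ-48 is scheduled before the subject has the device.
- **Step 2.04** makes advancement depend on that reading and on the eSight-8 of Step 2.03, that is, on the subject's "responses to 2.02 and 2.03 above the Eyecare Physician will determine whether or not the Subject ought to proceed".
- **The note to Step 2.04** picks out seven VFQ-48 items on which the device is thought to work especially well. Of subjects who rate four or more of them at moderate or extreme difficulty it says "they will be considered a strong candidate". It also says that this is not a formal inclusion criterion.
- **Step 3.09** is a second decision. It rests on the device demonstration, including a gain of at least four ETDRS lines.
- **Step 8.01** repeats the VFQ-48 by telephone 86-94 days after Step 4.
- **Section 10** reports the "comparison between the initial VFQ, and RAND SF-36 scores, and the change, if any, in score at the conclusion of the study", using repeated-measures ANOVA and t-tests or non-parametric counterparts. Its stated limitations are site differences and short follow-up. Section 4 describes no control group.
- **Section 3.1** sizes the extended arm at 60 for an effect of 0.40-0.45: "Power analysis indicates that in a single tailed test with an alpha level of .05 and a power of .95". On recruitment it says "we anticipate a total of 150-200 to be enrolled in screening arm of the study, from which 60 will be selected". About one third to one half of subjects meeting the acuity and field criteria are expected to "demonstrate acute objective improvement and an immediate aptitude with the device".

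**The concern.** A single questionnaire score is the subject's usual level plus reading error. Favouring subjects with poor scores favours, on average, subjects whose error ran in the poor direction that day. A later reading has fresh error, so the group mean moves back towards its usual level even if nothing was done.

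The reading that helps choose the subjects is also the one from which change is measured. The plan has no control group and no repeat baseline, and it does not mention regression to the mean. The artefact would therefore be counted as device benefit on the VFQ-48.

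Section 2 also aims to find which daily activities benefit most. The artefact would be strongest on the seven items used for selection, which are those where the sponsor already expects the most benefit.

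This is separate from the four-line ETDRS requirement at Step 3.09, which selects on acuity.

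**Working it through.** **1. The plan's own figure.** Read as a paired t-test (one-sided alpha 0.05, power 0.95, exact noncentral t), the required n is 70 at 0.40, 62 at 0.425, 60 at 0.43 and 55 at 0.45. So n=60 is reproduced at 0.43, inside the stated range. Normal check: ((1.645 + 1.645)/0.43)² = 58.5, i.e. 59. Power at n=60 is 0.922 at 0.40 and 0.964 at 0.45. The scale used below is the same: dz = mean change / SD of change.

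**2. How selective is Step 2.04?** The documents give no pass rate. From Section 3.1:
- All decisions together keep 60/200 = 30% to 60/150 = 40%.
- The one-third to one-half yield belongs to the device demonstration. Reaching 60 needs 60/(1/2) = 120 to 60/(1/3) = 180 subjects at that point.
- If the 150-200 are counted before Step 2.04, that step keeps at least 120/200 = 60%. At the other end 180/150 exceeds 100%, so the upper limit is 100%.
- If they are counted after Step 2.04, its pass rate is unknown.

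**3. Formulas.** The assumptions are normal scores, selection on the baseline score, test-retest correlation r between 0.7 and 0.9 (not in the documents), no device effect, and a Step 3.09 decision unrelated to VFQ-48 reading error. If a share p is kept, with cut-off c = Φ⁻¹(1−p):
- i = φ(c)/p
- shift = i(1−r), in SDs of the score
- V = 1 + c·i − i² (baseline variance among those kept)
- dz = shift / √[(1−r)²V + 1 − r²]
- chance of one-sided p<0.05 at n=60: noncentral t with 59 degrees of freedom and noncentrality dz·√60

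**4. Worked case: p = 80%, r = 0.8.** c = −0.842, i = 0.350, shift = 0.350 × 0.2 = 0.070, V = 1 − 0.295 − 0.122 = 0.583. SD of change = √(0.04 × 0.583 + 0.36) = 0.619. dz = 0.070/0.619 = 0.113. The chance of a significant result is 22%, against a nominal 5%.

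**5. Range.**

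| Kept at Step 2.04 | i | dz, r=0.7 | dz, r=0.8 | dz, r=0.9 | Chance of p<0.05 (r=0.9 to 0.7) |
|---|---|---|---|---|---|
| 100% | 0 | 0 | 0 | 0 | 5% |
| 90% | 0.195 | 0.077 | 0.063 | 0.044 | 10-15% |
| 80% | 0.350 | 0.140 | 0.113 | 0.079 | 15-28% |
| 60% | 0.644 | 0.261 | 0.210 | 0.146 | 30-64% |
| 40% | 0.966 | 0.395 | 0.317 | 0.220 | 52-92% |
| 30% | 1.159 | 0.476 | 0.381 | 0.264 | 65-98% |

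**6. Check against the actual rule.** Selection on four or more of seven items was simulated within a 48-item score, with an assumed item structure. For r = 0.7, 0.8 and 0.9 it gave dz 0.42, 0.33, 0.25 at about 31% kept; 0.29, 0.25, 0.16 at 50%; and 0.20, 0.16, 0.10 at about 69%. Using seven items rather than the total does not change the picture.

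**The case against.** The best defence is that Step 2.04 may hardly select at all. The note disclaims a formal criterion. It names strong candidates without saying that others are turned away. The decision is the physician's judgement and also uses the eSight-8. Section 3.1 points to the device demonstration as the main filter. If nearly everyone passes Step 2.04, the artefact is close to zero.

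This stands as a limit on size. It does not remove the mechanism, because the step itself names these answers as a basis for the decision, and the note says which direction is favoured.

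A reader might infer three stronger things, none of which the documents support:
- **That the artefact could equal the planned effect.** A dz of 0.4 or more needs nearly the whole 30-40% funnel to fall on Step 2.04, with r near 0.7. At r = 0.8 even 30% kept gives only 0.38. Section 3.1 also does not tie 0.40-0.45 to the VFQ-48.
- **That the main patient-reported outcome is affected.** No primary endpoint is named. Section 10 gives acuity, contrast and reading speed as the minimum, and lists the VFQ and SF-36 as further data.
- **That improvement is guaranteed without the device.** It is expected only as far as the decision follows the score.

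**Conclusion.** The point holds in a limited form. One VFQ-48 reading is both a basis for advancement and the baseline, more difficulty is favoured, and nothing in the plan separates regression to the mean from device benefit.

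If the 150-200 are counted before Step 2.04, the spurious dz is about 0 to 0.26. At 80% kept it is 0.08-0.14, which raises the one-sided error at n=60 from 5% to about 15-28%. Values of 0.4 or more are a worst case only.

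These figures rest on the assumed r of 0.7-0.9, on the decision following the score, and on a one-sided test of the VFQ-48 as in Section 3.1. Discretion at Step 2.04 moves the true value towards zero. This should be corrected, but it does not invalidate the study. Confidence in the size is medium, because neither the pass rate nor the reliability is documented.

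**What to change.** **Free (analysis wording only).** In Section 10, report next to the observed VFQ-48 change:

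(1−r) × (mean Step 2.02 score of subjects who passed Step 2.04 − mean Step 2.02 score of all who completed Step 2.02), for r = 0.7, 0.8 and 0.9.

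State that this part of the change is not attributed to the device. Give the Step 2.04 pass rate, and say whether the 150-200 are counted before or after that step.

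Two cautions apply:
- Do not put the extended-arm mean in place of the Step 2.04 mean. It also reflects Step 3.09, a different measurement, and true differences introduced there do not regress.
- Treat any split of the seven items from the other 41 as descriptive. True benefit may also be larger on the seven, so the split cannot isolate the artefact.

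**Optional, at small cost.** Repeat the telephone VFQ-48 once, after Step 2.04 and before the subject receives the device, and use it as the baseline. With independent reading errors the artefact from this step falls to about zero. The timing is a trade-off. Asking before the Step 3 demonstration avoids expectation effects but covers more subjects. Asking after Step 3.09 covers about 60 subjects and fits the 25-30 days before Step 4, but they have by then tried the device and know that they will receive it.

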3.2. Inclusion Criteria

1. Male or female subjects between the ages of 13-75. The goal for the extended arm is that 50% of subjects will be 65 years of age or younger, and 50% will be older than 65¹⁴.
2. Subject must have distance BCVA measured with ETDRS of between 20:60 and 20:400 in the better eye.
3. Subjects have been diagnosed with a condition that presents as one or all of the following: Central scotomata, geographic atrophy, or scattered scotomata. These are typically symptoms attributed to conditions such as: Diabetic Retinopathy, Stargardt's Disease, Age Related Macular Degeneration, Leber's Disease, Retinopathy of Prematurity, Cone Rod Dystrophy, or Ocular Albinism¹⁵.
4. Subject must have an estimated functional field of view of at least 20 degrees (bilateral or monocular).¹⁶
5. If the subject is employed, they must be prepared to use eSight Eyewear in their workplace environment, have informed their employer of their involvement in the study, and received permission from their employer to bring eSight Eyewear into the workplace. If the subject is self-employed, they must be prepared to use eSight Eyewear in their

¹³ "Sample size estimation and power analysis for clinical research studies", Suresh & Chandrashekar, J Hum Reprod Sci. 2012 Jan-Apr; 5(1): 7-13. "G*Power 3: a flexible statistical power analysis program for the social, behavioral, and biomedical sciences", Erdfelder, Faul, & Buchner, Behav Res Methods. 2007 May;39(2):175-91.

¹⁴ The intention of this stratification of the cohort is to understand age effects related to the eSight Eyewear device. This stratification does not impact the statistical analysis in Section 3.1

¹⁵ These have been demonstrated by current eSight users to be conditions for which eSight Eyewear can provide significant benefit. For other conditions, especially those which present as peripheral degeneration encroaching inwardly ultimately towards the central vision, eSight Eyewear's effectiveness has not yet been convincingly demonstrated (e.g.: early stage Retinitis Pigmentosa, early stage Glaucoma).

¹⁶ Acuity and field criteria, while firm requirements here, are inflection points in the real world population. Evidence indicates that eSight users outside of the 20/60 – 20/400 BCVA and 20° field can still have success with the eSight device, but results are less consistent.

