3.3. Exclusion Criteria

1. Subject must not be currently undergoing any medical or surgical procedures resulting in unstable vision.
2. Subjects for whom their vision, for whatever reason, can be considered unstable.
3. Subjects who have undergone cataract, refractive, or other surgical procedures related to vision in the six month period prior to the study.
4. Subjects who have undergone any eyesight-related injections (e.g. anti-VEGF) in the six month period prior to the study.
5. Subjects unable or unwilling to adhere to the examination schedules as they are described in the study protocol. This may also include Subjects already enrolled who, for whatever reason become unable or unwilling to continue the study. This may also include subjects for whom the travel time to/from the study site is unacceptable.
6. Subjects who self report a history of alcoholism or use of illegal drugs, Subjects who exhibit clinical evidence of depression, poor motivation, emotional or intellectual problems, who are deemed unsuitable psychologically or physiologically for study participation by the investigator.
7. Subjects who may have a conflict of interest with eSight Corp, which could reasonably influence their participation in the study.

4. Study Design

The Quality of Life and Functional Visual Improvement Study Using eSight Wearable Video Eyewear is a prospective multi-site study. The main elements of the study are shown in the flowchart below. Decision points are shown as diamonds. Note that the flowchart below only shows activity for the extended arm (n=60), not the larger screening arm.

As indicated on the chart, the red boxes are activities conducted by eSight. The green and blue boxes are conducted at the study site, by a research assistant, Occupational Therapist, Certified Low Vision Therapist or Eyecare Physician respectively (or supervised and trained designate). Over the course of the study there are four visits by the subject to the study site as indicated by the larger grey boxes. Tests conducted during the first visit are without the eSight device. Subsequent tests deploy the eSight device. Tests within each visit (grey boxes), do not necessarily need to be in the order presented above.

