Note: If, in the estimation of the researcher, the Subject identifies goals which are too abstract (e.g. “I want to do more”, “I want to be happier”), or not suitable uses for eSight Eyewear (e.g. “I want to swim”, “I want to drive”, “I want to go downhill skiing”), they will be encouraged to elaborate or identify a different goal that can be considered applicable to the Study/Device.

Step 3.02 Cognitive Assessment: To determine the cognitive capability of the subject to continue with the remainder of the study protocol, an assessment using the Montreal Cognitive Assessment – BLIND (MoCA)²⁰ test will be conducted. Psychometric properties of the MoCA in its full version include a test-retest correlation of $r = .92$, while internal consistency was evaluated with a Cronbach’s alpha of $.83$.²¹

While the cognitive suitability of the Subject for the test protocol is ultimately the decision of the researcher, a MoCA score of less than 20 indicates that careful consideration is necessary²². If the researcher determines that the subject is cognitively unsuited for the study, the remaining steps below are unnecessary (skip to 3.10).

Step 3.03 36-item short-form health survey (RAND SF-36)²³: The SF-36 is a brief questionnaire that provides a validated indication of the subject’s broad general health. It was chosen in part because of its excellent psychometric properties, which include a minimum of $.70$ for reliability statistics. Content, concurrent, construct, criterion, and predictive validity have been shown to be satisfactory (Ware & Gandek, 1998)²⁴

Steps 3.05 through 3.11 are administered by the Eyecare Physician or suitably trained and supervised clinical staff. These tests benchmark the subject’s visual performance with their habitual low vision aids where possible²⁵. As a minimum for these tests, the subject should wear their corrective lenses (distance or reading) as applicable. NOTE: if the lens prescription as

²⁰ “Sensitivity and Specificity of the Montreal Cognitive Assessment Modified for Individuals Who Are Visually Impaired”, Wittich, Phillips, Nasreddine, Chertkow, JVIB 06/2010; 104(6):360-368. See also: <http://www.mocatest.org>.

²¹ Nasreddine ZS, Phillips NA, Bedirian V, Charbonneau S, Whitehead V, Collin I, et al. The Montreal Cognitive Assessment, MoCA: a brief screening tool for mild cognitive impairment. J Am Geriatr Soc. 2005;53(4):695-9.]

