²² The MoCA scoring tool does not provide regarding pass/fail criterion. Ultimately, a subject’s performance in the test is meant to provide clues to the researcher about cognitive deficiencies.

²³ Ware, Sherbourne. “The MOS 36-item short-form health survey (SF-36). I. Conceptual framework and item selection”. Med Care. 1992 Jun;30(6):473-83.

²⁴ Ware JE, Gandek B. Overview of the SF-36 Health Survey and the International Quality of Life Assessment (IQOLA) Project. J Clin Epidemiol. nov 1998;51(11):903-12.

²⁵ References: The forms provided with this study are a subset of LV rehabilitation practice guidelines from the following sources:

- a) Ontario Practice Template - Low Vision Assessment.
- b) New York Lighthouse for the Blind LV Intake Exam ([name]) <http://www.lighthouse.org/professionals/practice-management/structured-low-vision-exam>.
- c) VisionAware: <http://www.visionaware.org/info/your-eye-condition/eye-health/low-vision/low-vision-examination/1235>

determined in step 1.04 is substantially different from the subject's habitual glasses, this portion of the protocol may be conducted with a trial lens frame.

Step 3.04 Medical and Ophthalmic History: The clinician and/or site administrator will record the following information on the CRF:

- OD and OS disease type(s), and approximate number of years, if possible.²⁶
- Free-form field: other eye-health related history (e.g.: laser photocoagulation, Lucentis, etc.), considered by the examiner to be relevant.
- subject's verbal description of visual scotoma if present

Step 3.05 Refractive Prescription: The clinician will perform a refraction to determine the prescription lenses required by the subject for best distance and near vision. Note: No prism element may be included in the refraction prescription.

Step 3.06 Acuity Test: Choose ONE OF ETDRS or Snellen

ETDRS²⁷: Using the subject's habitual corrective lenses (if applicable). For each eye independently, and then binocularly, determine the ETDRS acuity.

- Determine the last row where the subject can correctly identify all 5 letters on that row.
- Determine the log score for that row (these scores are shown in the margin of the ETDRS test, e.g. the 20/25 line has a log score of 0.1)
- subtract 0.02 log units for every letter that is correctly identified beyond the last row where all of the letters are correctly identified.

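### No scheduled reading has to be the best-corrected ETDRS acuity that Inclusion 2 and the 4-line criterion call for: Step 3.06 allows Snellen and specifies habitual lenses

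*Combined protocol and SAP*

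**What the plan says.** Section 3.2, item 2: "Subject must have distance BCVA measured with ETDRS of between 20:60 and 20:400 in the better eye". Footnote 16 treats the acuity and field limits as firm for this study.

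Section 4.1 sets out the measurements:

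- Step 1.03 has the Site Administrator check the inclusion and exclusion criteria before the clinic visit. It names no acuity measurement.
- At Step 3.05 the clinician is to "perform a refraction to determine the prescription lenses required by the subject for best distance and near vision".
- Step 3.06 is headed "Step 3.06 Acuity Test: Choose ONE OF ETDRS or Snellen". Both options specify habitual lenses. The ETDRS score starts from the last row on which all five letters are read. Footnote 28 explains the Snellen option: some subjects, for example with dense scotoma, may not complete any row.
- The text introducing these tests says that they benchmark "visual performance with their habitual low vision aids where possible". A note then allows an exception where the lens prescription "determined in step 1.04 is substantially different from the" habitual glasses: "this portion of the protocol may be conducted with a trial lens frame". Step 1 ends at 1.03, so the step it cites does not exist; the refraction is Step 3.05.
- Step 3.08 tests acuity with the device on ETDRS, for observation and not as a recorded baseline.
- Step 3.09 rechecks the entry criteria and weighs the four-line ETDRS gain together with task performance and the subject's impressions.
- Steps 4.02 and 9.03 repeat the acuity test, each again with either chart. Step 9.03 is done with and without the device.

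Section 4 adds: "Tests within each visit (grey boxes), do not necessarily need to be in the order presented above". Under Step 4.01a the subject's own device carries the lens prescription. The minimum report in Section 10 compares acuity without the device at the start with acuity with the device at the end.

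**The concern.** Acuity is an entry criterion, an input to advancement and a minimum reported outcome. The plan defines it in one way for entry and measures it in another.

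**Chart.** A subject read on Snellen at Step 3.06 has no scheduled ETDRS value to support Inclusion 2. For that subject the four-line gain has to be judged from a Snellen start to an ETDRS reading with the device. The fallback is aimed at subjects with scotoma, which is what Inclusion 3 recruits.

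**Lenses.** Habitual lenses need not give best-corrected acuity. If they are out of date and the trial frame is not used, the start-to-end change contains the benefit of the new prescription as well as that of the device. The change can still be computed, but it does not isolate the device.

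**Working it through.** **The protocol's own scale.** Its worked example is 0.20 − 3 × 0.02 = 0.14, which checks. One line is 0.20 − 0.10 = 0.10 logMAR (the 20/32 and 20/25 rows), or 5 letters at 0.02. Four lines are 0.40 logMAR, or 0.40 / 0.02 = 20 letters.

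**Required against scheduled, up to the Step 3.09 decision**

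| Need | Chart and correction required | What the schedule secures |
|---|---|---|
| Inclusion 2 | ETDRS, best-corrected | Step 1.03: no measurement named. Step 3.06: either chart, habitual lenses, optional trial frame |
| Four-line gain, starting value | ETDRS | Step 3.06: either chart |
| Four-line gain, device value | ETDRS | Step 3.08: ETDRS, not recorded as a baseline; lenses in the clinician's unit not stated |

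**Scoring.** A subject who reads 4 of 5 letters on each of six rows has read 6 × 4 = 24 letters, worth 24 × 0.02 = 0.48 logMAR. The all-five-letters rule has no row to start from and gives no score. Counting total letters does score this subject, so it removes the reason that footnote 28 gives for Snellen.

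**Refraction gain.** The documents give no figure. I assume 0.05 to 0.20 logMAR for a subject in outdated lenses:

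- 0.05 / 0.10 = 0.5 line (2.5 letters), and 0.05 / 0.40 = 12.5% of the four-line threshold.
- 0.20 / 0.10 = 2 lines (10 letters), and 0.20 / 0.40 = 50% of the threshold.
- With current correction the gain is 0.

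The lines and letters apply to the Section 10 comparison, because the subject's own device carries the prescription. The percentages apply to Step 3.09 only if the clinician's unit carries the new refraction, which is not stated.

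**Eligibility, only if the habitual-lens Step 3.06 value decides entry.** The limits are log10(60/20) = 0.477 and log10(400/20) = 1.301.

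- Better limit: 0.477 − 0.05 = 0.427 (20/53), and 0.477 − 0.20 = 0.277 (20/38). A subject with true best-corrected acuity of 20/53 to 20/38 would read 20/60.
- Worse limit: 1.301 + 0.05 = 1.351 (20/449), and 1.301 + 0.20 = 1.501 (20/634). A subject with true best-corrected acuity of 20/400 would read 20/449 to 20/634.

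**Effect on a group mean.** If 10% to 30% of subjects were affected (assumed), the mean shift would be 0.10 × 0.05 = 0.005 to 0.30 × 0.20 = 0.06 logMAR, or 0.25 to 3 letters.

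**The case against.** The strongest case is that habitual correction is deliberate. Footnote 11 defines functional performance against the subject's usual aids, Steps 3.11 to 3.13 also use habitual correction, and the device is supplied with prescription lenses. Device-as-supplied against habitual correction is a legitimate practical contrast. This stands: the contrast needs a label, not removal. It does not supply the best-corrected value that Inclusion 2 names.

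Second, eligibility is checked at Step 1.03, for candidates whom the Eyecare Physician selects from the site's patients, and Step 3.09 only confirms that it continues. A best-corrected value from clinic records may be used, and the case report form, which is not among the documents, may say so. A reader might infer that the protocol will admit or refuse the wrong subjects. The documents do not support that, because they never say that the Step 3.06 value decides entry. What remains is that no scheduled reading has to be the defined one.

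Third, the trial-frame note covers the case where the prescription has changed most. That reduces the risk. However, the note is permissive, sets no threshold for a substantial difference and cites a missing step.

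Fourth, test order matters little. Using the note presupposes that refraction has been done, and with habitual lenses order is irrelevant. I accept this; order matters only for the reading proposed below.

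Fifth, Steps 4.02 and 9.03 are described as repeats, which implies the same chart and perhaps the same lenses. That is a fair reading, but neither is required.

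**Conclusion.** The inconsistency is real, and the plan should correct it. Inclusion 2 and the four-line criterion call for an ETDRS value, best-corrected for Inclusion 2, that the schedule does not secure. Subjects read on ETDRS throughout with current correction are not affected by the chart or lens points.

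The lens effect is 0.5 to 2 lines per affected subject on an assumed gain of 0.05 to 0.20 logMAR. The number affected cannot be derived from the documents. The eligibility shifts need the further assumption that Step 3.06 decides entry, and the bearing on the four-line criterion needs the clinician's unit to carry the new refraction.

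A reader might go further and conclude that the acuity benefit could be an artefact of new glasses. The documents do not support that. On the illustrative mix above the mean shift is at most 3 letters, whereas advancement weighs a gain of at least 20. That gain is only one input to a partly personal decision, so it does not guarantee a large device effect, but reversal of the overall acuity conclusion is unlikely.

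**What to change.** Reconcile Inclusion 2 with Step 3.06:

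- At Step 3.06, after the Step 3.05 refraction, record without-device ETDRS acuity with that refraction in a trial frame, scored by total letters read at 0.02 each. Use it for Inclusion 2 and as the starting value for the four-line criterion. State this order, since Section 4 leaves it free.
- Keep habitual-lens acuity as a separately labelled benchmark, in line with Steps 3.11 to 3.13. Label any Section 10 comparison that uses it as device-as-supplied against habitual correction.
- Use the same chart for each subject at Steps 3.06, 4.02 and 9.03. State the correction for the Step 9.03 reading without the device, so that device gain can also be reported at equal correction.
- If Snellen stays as a fallback, report those subjects separately.
- Note on the case report form the Step 3.08 ETDRS result used for the decision and the lenses worn, as support for the decision and not as a baseline outcome.
- Change the reference to step 1.04 to Step 3.05.

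Cost: protocol and form wording, and trial-frame set-up. The refraction, trial frame and ETDRS chart are already in the plan. Keeping both lens conditions adds up to 3 readings per subject (each eye, then binocular). Section 3.1 says "we anticipate a total of 150-200 to be enrolled in screening arm of the study", so that is 3 × 150 = 450 to 3 × 200 = 600 readings at Step 3.06, and 3 × 60 = 180 at Step 9.03 if both are repeated there. The reported acuity gain may be smaller. The target of 60 does not change.
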